## 8.2 Bone Marrow for Flow Cytometry of Measurable Residual Disease (MRD) (Required)

### 8.2.1 Description of Studies and Assay

Bone marrow MRD will be evaluated at the end of each cycle using flow cytometry for disease assessment. Samples should be sent directly to Hematologies Inc. following the instructions below. If the MRD sample is not evaluable per Hematologies, sites will be informed. It is critical that a repeat bone marrow examination should be performed until a result can be obtained. Optimally, a specimen should be submitted while a patient has an absolute neutrophil count (ANC) greater than 200/uL. If possible, a repeat bone marrow aspirate is recommended once the ANC has recovered.

### 8.2.2 Sampling Schedule

Bone marrow samples are required to be sent for MRD analysis at the following time points:

- End of Cycle 1
- End of Cycle 2

### 8.2.3 Sample Collection and Handling Instructions

A bone marrow aspirate is required for MRD testing. Collect a minimum of 2 - 4 mL of bone marrow in a preservative-free **sodium heparin vacutainer (green top)**. Samples cannot be submitted in EDTA or shipping media as they compromise key antigens.

If sample cannot be shipped immediately (i.e., sample is drawn on a Saturday, Sunday or holiday), **store sample with equal volume of RPMI medium at room temperature and ship on the next business day.** It is recommended to use RPMI without EDTA if available.

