
## EXPERIMENTAL DESIGN SCHEMA

**Table 1 – Experimental Design Schema**

Each Cycle (28 days)						
	Uproleselan (GMI-1271) IV	Fludarabine IV	Cytarabine IV	Cytarabine IT	IT Triples	Leucovorin PO or IV
Day 0				once daily 	once daily 	
Day 1	once daily					24 and 30hrs post ITT 
Day 2	q12hr	once daily	once daily			
Day 3	q12hr	once daily	once daily			
Day 4	q12hr	once daily	once daily			
Day 5	q12hr	once daily	once daily			
Day 6	q12hr	once daily	once daily			
Day 7	q12hr			Weekly 	Weekly 	
Day 8	q12hr					24 and 30hrs post ITT 
Day 9						
...						
Day 14				Weekly 	Weekly 	
Day 15						24 and 30hrs post ITT 
Day 21				Weekly 	Weekly 	
Day 22						24 and 30hrs post ITT 
Day 28				Weekly 	Weekly 	
Day 29 						24 and 30hrs post ITT 

 Choice between IT Cytarabine OR IT Triples is up to the treating physician's discretion. Weekly intrathecal chemotherapy treatments are for CNS 2/3 patients ONLY. A minimum of 4 and a maximum of 6 intrathecal treatments may be given (count includes day 0 IT and may carry over into Cycle 2 of chemotherapy).

 Down syndrome patients ONLY. Administer 24 & 30 hours after each IT Triples.

 End of cycle bone marrow for disease assessment may be performed any day between Day 28-35.

 Day 28 lumbar puncture can be done at the same time as the end of cycle bone marrow assessment between day 28-35.

A cycle of therapy is considered to be 28 days. Upon count recovery, patients may receive a second cycle of uproleselan (GMI-1271) in combination with fludarabine and cytarabine if there is evidence of clinical benefit in the opinion of the treating physician and eligibility criteria are met for organ function criteria.

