### 8.2.5 Sample Shipping Instructions

Samples should be shipped immediately to arrive next day to Hematologies Inc. Seattle, WA at the address listed below. All specimens sent to Hematologies Inc. must be accompanied by PEPN2113 Bone Marrow MRD specimen transmittal form.

Ship samples by FedEx Priority Overnight Using the COG FedEx account listed in the FedEx Account Usage Guidelines: <https://members.childrensoncology>

THIS PROTOCOL IS FOR RESEARCH PURPOSES ONLY, SEE PAGE 1 FOR USAGE POLICY

[group.org/\\_files/reference/FEDEXmemo.pdf](http://group.org/_files/reference/FEDEXmemo.pdf). Be sure to indicate the samples are for PEPN2113 on the FedEx air bill.

Hematologics, Inc.  
[name]  
[name]  
[contact] or [contact]  
[contact]  
Weekends and After Hours: [contact]

**Weekend Specimens:** The lab is staffed 6 days a week. For Saturday delivery, please use a *Saturday delivery* sticker and check the *Saturday delivery* box on the address label. Both sticker and checked box are necessary to insure proper handling.

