### **MRD negative:**

Presence of < 0.05% of leukemic blasts by flow cytometry.

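### Section 8.2.3 bans EDTA and shipping media for MRD marrows, then lets weekend and holiday samples be held and shipped in RPMI that may contain EDTA

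*Combined protocol and SAP*

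**What the plan says.** Section 8.2.3 asks for the marrow in a preservative-free heparin tube and then sets a ban with its reason: "Samples cannot be submitted in EDTA or shipping media as they compromise key antigens".

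For a sample that cannot leave at once, which the section explains as one drawn on a Saturday, Sunday or holiday, the instruction is: "store sample with equal volume of RPMI medium at room temperature and ship on the next business day". The only statement about the composition of that medium is: "It is recommended to use RPMI without EDTA if available".

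Three other provisions bear on this:

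- Section 8.2.1 covers samples that the laboratory cannot evaluate: "It is critical that a repeat bone marrow examination should be performed until a result can be obtained".
- Section 8.2.5 says of the laboratory: "The lab is staffed 6 days a week", and explains how to request Saturday delivery.
- Table 1, footnote 3, gives the timing: "End of cycle bone marrow for disease assessment may be performed any day between Day 28-35".

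**The concern.** The two paragraphs of Section 8.2.3 cannot both be followed. The first is absolute. The second allows EDTA for one subset of required samples whenever EDTA-free RPMI is not at hand. It also has those samples travel in a medium, without saying whether RPMI falls under the ban.

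The assay reads antigens. Section 2.5.1 describes the same laboratory's method as one that finds blasts by how their antigen pattern differs from normal. A handling step said to harm antigens could therefore alter the result, and it would do so only for samples drawn on particular days.

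Central MRD is used in three places:

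- **Aim 1.2.2.** The MRD-negative rate is a named part of this secondary aim.
- **Complete remission.** For patients enrolled with under 5% blasts, Section 12.2.2 and Appendix VIII accept only MRD-negative remission. Appendix VIII counts failure to reach it as treatment failure.
- **Hematological DLT.** Section 5.5.2.1 excludes failed count recovery that is due to leukemia, including disease seen only as MRD on central flow. This touches a primary aim.

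**Working it through.** The plan gives no figure on this point, so there is none to reproduce. The check is a comparison of texts followed by illustrative arithmetic.

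**1. Do the paragraphs conflict?** The first forbids EDTA and shipping media. The second prescribes RPMI for held samples and makes its EDTA-free form a recommendation that depends on supply. No step removes the medium before shipping, and no sentence exempts RPMI. They conflict.

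**2. Do the other provisions close the gap?**

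| Provision | What it covers | What it leaves open |
|---|---|---|
| Repeat marrow (8.2.1) | Samples the laboratory calls not evaluable | A degraded sample that is still reported |
| Saturday delivery (8.2.5) | A Friday draw | Saturday, Sunday and holiday draws |
| Day 28-35 window (Table 1) | Makes a weekday draw feasible | Nothing asks sites to use it that way |
| Draw date on the label (8.2.4) | Identifies weekend draws | The medium used |

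The window is 8 consecutive days. Seven of them always hold 5 weekdays, and the eighth falls on the same weekday as the first, so the total is 5 or 6. Public holidays can lower it.

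**3. What does one misclassified patient weigh?** The weight is 1/n. Section 11 suggests the sizes: 6 + 6 = 12 (one dose level plus the PK cohort) and 6 + 6 + 6 = 18 (two dose levels plus the PK cohort).

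- n = 12: 1/12 = 8.3 points
- n = 18: 1/18 = 5.6 points
- n = 22 (expected maximum, Section 11.1): 1/22 = 4.5 points

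These are the effects of one error. They say nothing about how likely it is.

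**4. How much blast signal must be lost to turn a positive negative?** Appendix VIII sets MRD negativity at under 0.05% "of leukemic blasts by flow cytometry". If the true blast percentage is b, the share of blasts that must go unseen is more than 1 - 0.05/b.

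| True blasts, b | Loss needed |
|---|---|
| 0.06% | 17% |
| 0.1% | 50% |
| 0.25% | 80% |
| 0.5% | 90% |
| 1% | 95% |

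Only low-level disease is easily flipped.

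**5. Can a rate be derived?** No. The number of false negatives would be the product of four things: patients with residual disease, the share of draws on a weekend or holiday, the share of those held in RPMI with EDTA, and the share of those flipped. The documents give none of them. As an assumption, take 22 patients with one residual-positive marrow each, a share w held in RPMI with EDTA, and a share q of those falsely negative. The expected number is 22wq, and the chance of at least one is 1 - (1 - wq)^22.

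- w = 0: none
- w = 1/7, q = 5%: 22 x 0.00714 = 0.16 expected; chance 0.15
- w = 2/7, q = 25%: 22 x 0.0714 = 1.57 expected; chance 0.80

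The range is too wide to serve as an estimate.

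**6. DLT route.** A false-negative MRD could turn an excluded count failure into a counted DLT if no other exclusion applies. A false positive could do the reverse. Under Section 11.3, one DLT among six evaluable patients at Dose Level 1 makes that level the recommended dose. Two exceed the MTD, subject to the exception in Section 11.2.2. One misread marrow could therefore matter, although it would need to coincide with failed count recovery.

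**The case against.** The strongest reply is that this is a wording conflict with little demonstrated effect.

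- **Direction and size are unknown.** The documents do not name the antigens affected, the signal lost or the direction. Damage could hide blasts, make normal cells look abnormal, or make the sample unreadable. The last outcome triggers a repeat. This stands, and it limits the conclusion.
- **Exposure may be rare.** Samples are still drawn in heparin, nothing says how often sites would hold RPMI with EDTA, and a scheduled marrow that may be combined with the Day 28 lumbar puncture is unlikely to fall evenly over the week. This also stands.
- **The response analyses are descriptive.** Section 11.4 says so, and no efficacy decision depends on them. This is true for aim 1.2.2 but does not cover the DLT exclusion.
- **The form may already record the medium.** The transmittal form is not in the documents, so this cannot be ruled out.

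A reader might go further and infer that handling produces MRD negativity, or that 2/7 = 29% of samples are exposed. The documents support neither. The first assumes a direction that they do not give. The second is the share of draws at a weekend if draws were spread evenly, not the share that meets EDTA.

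None of this reconciles the two paragraphs, and a degraded sample that still gives a value escapes the repeat rule.

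**Conclusion.** Section 8.2.3 contradicts itself, and the contradiction should be removed. A site that follows it can submit a required marrow in a condition that the protocol says compromises the antigens. The consequence is a possible bias or loss of quality in central MRD for weekend and holiday samples, of unknown direction and size.

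Any effect on aim 1.2.2 would be coarse, because each misclassified patient moves the rate by 8.3 points in 12 or 5.6 in 18. The remission definition for patients enrolled with under 5% blasts and the DLT exclusion use the same readout.

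The contradiction itself rests on the text alone. That it matters for results rests on taking the protocol's own statement about antigens at face value, and on at least some sites using RPMI with EDTA.

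**What to change.** Amend Section 8.2.3, in agreement with the central laboratory:

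1. Require that any RPMI used is EDTA-free, and state that this RPMI is exempt from the shipping-media ban.
2. Ask sites to draw the end-of-cycle marrow on a weekday inside the existing Day 28-35 window where feasible, so that it ships the same day.
3. Record the medium and holding time on the transmittal form if it does not already capture them. Flag any EDTA-exposed sample in the MRD summary, and let the central laboratory decide whether it is evaluable.

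Exposed samples should not be scored automatically as not evaluable. Read with Section 8.2.1, that would call for a repeat marrow in a child even where the laboratory has a readable result.

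The cost is one paragraph of amendment text, at most one extra form entry for medium and holding time, and slightly less freedom in choosing the marrow day.

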### 8.2.4 Sample Labeling

Clearly label the tube as bone marrow aspirate (BMA) or peripheral blood (PB) along with study ID, COG number, patient DOB, and date sample was obtained.

### 8.2.5 Sample Shipping Instructions

Samples should be shipped immediately to arrive next day to Hematologies Inc. Seattle, WA at the address listed below. All specimens sent to Hematologies Inc. must be accompanied by PEPN2113 Bone Marrow MRD specimen transmittal form.

Ship samples by FedEx Priority Overnight Using the COG FedEx account listed in the FedEx Account Usage Guidelines: <https://members.childrensoncology>

THIS PROTOCOL IS FOR RESEARCH PURPOSES ONLY, SEE PAGE 1 FOR USAGE POLICY

[group.org/\\_files/reference/FEDEXmemo.pdf](http://group.org/_files/reference/FEDEXmemo.pdf). Be sure to indicate the samples are for PEPN2113 on the FedEx air bill.

Hematologics, Inc.  
[name]  
[name]  
[contact] or [contact]  
[contact]  
Weekends and After Hours: [contact]

**Weekend Specimens:** The lab is staffed 6 days a week. For Saturday delivery, please use a *Saturday delivery* sticker and check the *Saturday delivery* box on the address label. Both sticker and checked box are necessary to insure proper handling.

### 8.3 Pharmacology (Required)

#### 8.3.1 Description of Studies and Assay

Pharmacokinetic analysis of uproleselan (GMI-1271) will be performed by GlycoMimetics. Plasma samples will be obtained at specific timepoints as indicated in the Specimen Collection table below. PK studies will be determined by a validated LC/MS/MS method.

#### 8.3.2 Sampling Schedule

Plasma samples will be obtained at the following time points during Cycle 1:

8.3.2.1 For patients  $\geq 10\text{kg}$ , blood samples will be obtained prior to drug administration and at the following time points:

**Table 9A – Pharmacology Sampling Schedule (for patients > 10kg)**

Day	Timepoint
Cycle 1 Day 1 (1 st dose of uproleselan (GMI-1271))	Immediately pre-dose ( $\pm 20$ minutes)*
	30 minutes ( $\pm 5$ minutes)*
	1 hours ( $\pm 20$ minutes)*
	2 hours ( $\pm 20$ minutes)*
	4 hours ( $\pm 20$ minutes)*
Cycle 1 Day 6 (1 st dose of day)	Immediately pre-dose ( $\pm 20$ minutes)*
	30 minutes ( $\pm 5$ minutes)*
	1 hours ( $\pm 20$ minutes)*
	2 hours ( $\pm 20$ minutes)*
	4 hours ( $\pm 20$ minutes)*

\* time-points are relative to start of infusion

THIS PROTOCOL IS FOR RESEARCH PURPOSES ONLY, SEE PAGE 1 FOR USAGE POLICY

8.3.2.2 For patients < 10 kg samples will be obtained prior to drug administration and at the following time points:

**Table 9B – Pharmacology Sampling Schedule (for patients < 10kg)**

Day	Timepoint
Cycle 1 Day 1 (1 st dose of uproleselan (GMI-1271))	Immediately pre-dose (±20 minutes)*
	30 minutes (±5 minutes)*
	1.5 hours (±20 minutes)*
	4 hours (±20 minutes)*
Cycle 1 Day 6 (1 st dose of day)	Immediately pre-dose (±20 minutes)*
	30 minutes (±5 minutes)*
	1.5 hours (±20 minutes)*
	4 hours (±20 minutes)*

\* time-points are relative to start of infusion

### 8.3.3 Sample Collection and Handling Instructions

Blood samples

- 2 mL for patients ≥6 years
- 1 mL for patients <6 years

Blood samples will be collected in sodium citrate tubes at a site distant from the infusion for pharmacokinetic evaluation. Care should be taken that blood for PK assessment is drawn from a vein apart from the site of uproleselan (GMI-1271) infusion (e.g., from a different limb or central line).

1. Drawing from the same line as drug infusion even with a second lumen is not recommended as there is a high likelihood of getting high concentrations. It is recommended to either establish a separate line in the opposite arm or collect via individual venipuncture from the opposite arm.
2. If separate line cannot be established, it is preferred to draw samples peripherally
3. If multiple peripheral sticks are not feasible due to venous access or patient refusal, prioritize peripheral collection of the 30 min dose sample
4. If separate line or peripheral sticks are not at all possible, draw from double lumen
5. If drawing multiple samples from an intravenous (IV) line, before taking the blood sample, a 'discard' tube must be taken to clean the IV line.

Samples cannot be drawn from the 2nd lumen of a multi-lumen catheter through which drug is being administered. Record the exact time that the sample is drawn along with the exact time that the drug is administered. If study drug is diluted, record dilution volume used.

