### 5.1.1 Uproleselan (GMI-1271): IV over 20 minutes (±2 minutes)

Days: 1-8

On Day 1, uproleselan (GMI-1271) will be administered as a single dose 24 hours ± 2 hours prior to the first dose of chemotherapy. Since patients will receive a single dose of IT cytarabine or ITT on Day 0 of Cycle 1, it is recommended, but not required, that systemic therapy begin at least 24 hours after the intrathecal therapy.

On Days 2-6, uproleselan (GMI-1271) will be administered every 12 hours ±1 hour starting 2 hours ± 15 minutes *prior* to initiation of chemotherapy (fludarabine and cytarabine).

On Days 7-8, uproleselan (GMI-1271) will be administered every 12 hours ±1 hour as single agent.

At least 22 hours ± 2 hours should pass between uproleselan (GMI-1271) dose on Day 1 and the first uproleselan (GMI-1271) dose on day 2. A total of 15 uproleselan (GMI-1271) doses will be administered on Days 1-8.

If ≤6 hours have elapsed since the time of the planned dose, the dose should be given. If uproleselan (GMI-1271) and chemotherapy are held for more than 72 hours for medical reasons, the study chair or vice chair should be consulted before restarting uproleselan (GMI-1271). If chemotherapy is held for less than 72 hours and is restarted, uproleselan (GMI-1271) may be restarted when chemotherapy is restarted, and the original schedule continued if possible. For questions on restarting uproleselan (GMI-1271), the chair or vice chair should be consulted.

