#### 11.2.2 Maximum Tolerated Dose

- The MTD will be the maximum dose at which fewer than one-third of patients experience DLT (See [Section 5.5](#)) during Cycle 1 of therapy.
- In the unlikely event that two DLTs observed out of 6 evaluable patients are different classes of Adverse Effects (eg, hepatotoxicity and myelosuppression), AND all of the following conditions are met, expansion of the cohort to 12 patients will be considered:
  - One of the DLTs does not appear to be dose-related
  - The Adverse Effects are readily reversible
  - The study chair, PEP-CTN statistician, PEP-CTN committee chair or vice chair, and IND sponsor all agree that expansion of the cohort is acceptable
- The DLTs observed in the pharmacokinetic (PK) expansion cohort will be counted towards the total number of DLTs observed at the MTD. If  $\geq 1/3$  of the cohort of patients at the MTD (during the dose evaluation plus the PK expansion) experience DLT then the MTD will be exceeded.

THIS PROTOCOL IS FOR RESEARCH PURPOSES ONLY, SEE PAGE 1 FOR USAGE POLICY

- If the maximum dose level (DL1) is safe (i.e., less than 1/3 of patients experience a Cycle 1 DLT among 6 DLT-evaluable patients), then DL1 will be the RP2D.
- Patients enrolled in the PK expansion cohort will be replaced if unevaluable for PK analysis defined as pre-dose, 30 minutes and 2 hrs after the dose on days 1 and 6 for patients with weight  $\geq 10$  kg; pre-dose, 30 minutes and 1.5 hrs after the dose on days 1 and 6 for patients with weight  $<10$  kg

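### The PK sampling rules contradict each other on drawing through the infusion catheter and on what counts as a pre-dose sample, so clearance estimates can be biased in either direction

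*Combined protocol and SAP*

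**What the plan says.** **Draw site.** Section 8.3.3 gives a numbered list and then a closing paragraph. Item 1 advises against the infusion line: "Drawing from the same line as drug infusion even with a second lumen is not recommended as there is a high likelihood of getting" (the sentence ends by naming elevated concentrations). Item 4 gives the fallback: "If separate line or peripheral sticks are not at all possible, draw from double lumen". The closing paragraph states that samples cannot come from the second "lumen of a multi-lumen catheter through which drug is being administered". Under 8.3.5 the tube carries the registration number, study ID, time point, and date and time of draw. The worksheets in Appendix VII-A and VII-B record weight, dose, draw date and time, and infusion start and stop. None of these has a field for the draw site.

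**Pre-dose sample.** In Tables 9A and 9B the row reads "Immediately pre-dose (±20 minutes", with the footnote "time-points are relative to start of infusion". Section 5.1.1 gives uproleselan "IV over 20 minutes (±2 minutes". The lead-ins at 8.3.2.1 and 8.3.2.2 say this sample precedes drug administration. The worksheets list it with no tolerance, although every other row there carries one.

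**Use.** Pharmacokinetics is primary aim 1.1.2. Section 2.5.2 bases the RP2D on clearance within 30% of adults and on exposure, and 5.3.1 makes Dose Level 2 depend on the same margin. Section 11.4 plans descriptive PK summaries and gives no rule for suspect samples.

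**The concern.** A site whose patient has only a multi-lumen line is told both to use it and not to use it. Different sites will resolve this differently. The protocol names the consequence itself: concentrations that read too high. If the PK forms do not show where a sample came from, the analyst working from them cannot separate a contaminated value from a genuine one.

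The pre-dose window is a second inconsistency. Read literally, its plus side reaches the end of infusion, which is close to peak concentration. That would lose the Day 1 baseline or the Day 6 trough.

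Section 2.5.2 considers it unlikely that DLTs will determine the RP2D and puts the weight on clearance. Section 11.3 allows up to six patients plus up to six in the PK cohort at that dose, so a few bad profiles carry weight. Bias in clearance could hide a genuine 30% difference from adults or create an apparent one.

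**Working it through.** **Plan figure.** No stated figure is in dispute. The one number tied to PK evaluability, the expected maximum of 22 in 11.1, reproduces as (6 × 2 + 6) × 1.2 = 21.6, rounded up to 22. This point does not change it.

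**Draw-site text side by side.** Using the second lumen is discouraged in item 1, instructed in item 4 when nothing else is possible, and prohibited in the closing paragraph. Items 1 and 4 fit together as an order of preference. Item 4 and the prohibition do not.

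**Inputs for the illustration.** The infusion lasts T = 1/3 h (5.1.1) and sample times are those in Table 9A or in the 11.2.2 minimum set. The human half-life h is not given: 2.3.2 calls it short, and 2.2.4 gives about 1 h in mice. I assume 1, 2 and 3 h. The contamination factor is also assumed.

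**Model.** One compartment with k = ln2/h. After the infusion, C(t) = (e^(kT) − 1)/(kT) × e^(−kt). Clearance is dose/AUC, using the linear trapezoid plus C(last)/k estimated from the last two points.

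*Worked case, h = 3 h, 30-minute value doubled.* True values: C(0.5) = 0.926, C(1) = 0.825, C(2) = 0.655, C(4) = 0.413, k = 0.231.

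- Full schedule, clean: AUC = 0.232 + 0.438 + 0.740 + 1.068 + 0.413/0.231 = 4.26. Doubling adds 0.926 × 0.5 = 0.463, giving 4.73. The slope still comes from 2 h and 4 h. Clearance factor: 4.26/4.73 = 0.90.
- Minimum set (pre-dose, 30 min, 2 h), clean: AUC = 0.232 + 1.186 + 0.655/0.231 = 4.25. Doubled: the slope becomes ln(1.852/0.655)/1.5 = 0.693, so AUC = 0.463 + 1.880 + 0.655/0.693 = 3.29. Clearance factor: 4.25/3.29 = 1.29.

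Apparent clearance relative to the same samples uncontaminated:

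| Case | h = 1 | h = 2 | h = 3 |
|---|---|---|---|
| 30-min × 2, full schedule, ≥10 kg | 0.78 | 0.86 | 0.90 |
| 30-min × 2, minimum set, ≥10 kg | 0.69 | 0.99 | 1.29 |
| 30-min × 2, minimum set, <10 kg | 0.82 | 1.24 | 1.66 |
| All samples × 2 | 0.50 | 0.50 | 0.50 |

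If every sample is raised m-fold, the factor is 1/m: 0.80, 0.67 and 0.50 for m = 1.25, 1.5 and 2.

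**Against the 30% margin.** A child who truly clears 30% faster would appear at 1.30 × 0.80 = 1.04 of adult clearance if all samples read 1.25 times too high. A child with adult clearance would appear at 1.29 in the worked minimum-set case. These are per-patient effects. If a share p of patients has factor r and the rest are clean, a cohort mean of equal true clearances moves to 1 − p(1 − r). With 3 of 12 patients at r = 0.50, that is 1 − 0.25 × 0.50 = 0.875.

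**Pre-dose window.** A draw at +20 minutes falls at end of infusion. Relative to the 12-hour trough it reads e^(k(12 − 1/3)) = 2^(11.67/h), about 3,250, 57 and 15 times for h = 1, 2 and 3 h. The effect on clearance is far smaller: if that value is entered at time zero and the recorded time ignored, clearance on the full schedule falls about 14%, 8% and 5%. Analysing it at its recorded time largely removes the error, but the baseline or trough is still lost.

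**The case against.** **Catheter rule.** The prohibition could be read as applying only while drug is running. Every nominal post-dose time falls after the 20-minute infusion, so on that reading item 4 could survive. The text does not say this, and item 1's warning is not limited to the infusion period. Item 3 gives the 30-minute sample priority for peripheral collection, which helps but covers one time point.

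**Traceability.** A reader might infer that contaminated samples could never be identified. The documents do not support that: the CRF packet is separate (14.1), and 14.4 describes source data verification for all patients. What stands is that the PK worksheets and tube labels would not identify them.

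**Pre-dose window.** A reader might infer that the protocol authorises a draw during the infusion. The lead-ins in 8.3.2 and the worksheets say otherwise, so this is an inconsistency introduced by a ± sign. Recorded draw and infusion times would expose a late sample.

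**Direction.** A reader might infer that contamination only lowers clearance and so masks faster clearance in children. The table shows both signs, because with two post-dose points a raised 30-minute value steepens the terminal slope.

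**The 4-hour sample.** A reader might also object that it is missing from the essential set in 11.1 and 11.2.2. It is scheduled and required for every patient (8.3, Appendix V), and the essential set is only a replacement threshold. Section 2.5.2 plans to update the adult population PK model with these data. In the one-compartment model, clearance from uncontaminated samples at pre-dose, 30 minutes and 2 hours is within about 2% of true. An assumed two-compartment disposition would give a larger error, but the documents give no human values to support one. Enlarging the set would cost evaluable children in a trial of about 22.

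**Conclusion.** Two defects stand on the text alone. Section 8.3.3 both instructs and prohibits a second-lumen draw, with no draw site recorded on the PK forms. Tables 9A and 9B give the pre-dose sample a window that conflicts with 8.3.2 and with the worksheets.

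The first matters more. Recorded times would largely correct a mistimed sample, but neither they nor a population model repairs a contaminated one.

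Contamination can bias clearance in either direction, depending on which samples are affected and which are available. The factors shown (0.50 to 1.66 per patient for a doubling) rest on assumed half-lives of 1 to 3 hours, one compartment, non-compartmental estimation and an arbitrary contamination factor. They show that the bias could reach the 30% margin. They do not estimate how often or how far it would.

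**What to change.** 1. Reconcile the list and the closing paragraph of 8.3.3 into one sampling rule. If the prohibition is meant to apply only while drug is running, say so.
2. Add a draw-site field for each sample to Appendix VII-A and VII-B.
3. State in 11.4 that samples drawn through the infusion catheter are flagged and left out of the primary clearance estimate, with a sensitivity analysis that includes them.
4. Change the pre-dose window in Tables 9A and 9B to -20 to 0 minutes relative to the start of infusion.

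The cost is wording, one worksheet field and one analysis rule. No blood draws are added, and the essential sample set and planned enrollment stay as they are. The downside is that a few samples may drop out of the primary PK analysis, mainly in children with poor venous access. The sensitivity analysis keeps their data in view.
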